8.3 Statistical methods

Images collected during the fMRI odor cue reactivity task will be preprocessed using a standard Functional Magnetic Resonance Imaging of the Brain Software Library (FSL) software pipeline. Blood oxygen level dependent (BOLD) activation during the tobacco, strawberry vanilla, and rose flavors will be modeled using a double-gamma hemodynamic response function, contrasted to one another, and merged across the two runs for each participant. To create images that capture changes from baseline to post-conditioning, a difference z- statistic image will be calculated by subtracting the baseline image from the post-conditioning image. The lavender odor is an experimental control condition that encourages participants to maintain attention and task engagement during the MRI scan. It is not part of the endpoints of the study.

Aim 1: Determine if smokers and ECIG users have pre-conditioned neural cue-reactivity to tobacco or strawberry-vanilla ECIG odors. One- sample t-test will be conducted on the contrast of tobacco > strawberry vanilla, tobacco > rose, strawberry vanilla > rose to identify anatomical brain regions where tobacco elicits greater neural activation over strawberry vanilla and rose odors and strawberry vanilla elicits greater activation over rose odors. We expect tobacco odor to elicit greater activation in the ventral striatum, amygdala, anterior insula, and OFC than the strawberry vanilla and rose for combustible cigarette smokers and tobacco-flavored e-cigarette users. We expect strawberry-vanilla odor to elicit greater activation in ventral striatum, amygdala, anterior insula, and OFC than tobacco and rose for fruit-flavored e-cigarette users.

Aim 2: Examine the effect of flavor and nicotine on ECIG odor cue-reactivity after conditioning. Two-sample t-test will be conducted in FSL for the strawberry vanilla>rose and tobacco>rose odor difference score z- statistic images comparing the 18 mg to 0mg nicotine content ECIG groups. A paired two-sample t-test will be conducted to compare the tobacco>rose and strawberry vanilla>rose odor difference score z-statistic image separately for each 18 mg/ml ECIG flavor group. These t-tests will identify anatomical regions with significant effects of nicotine level and assigned vs. unassigned flavor over time. We expect that BOLD activity in regions implicated in smoking cue-reactivity will increase more over the conditioning phase for the 18 mg nicotine group compared to the 0mg nicotine group and for odors from the assigned vs. unassigned flavor.

Aim 3: Determine if strawberry vanilla results in stronger cue-reactivity than tobacco flavor. A two-sample t-test will be conducted for the assigned flavor (strawberry vanilla or tobacco) > control rose difference score z- statistic images comparing the flavor groups. These t-tests will identify anatomical regions with significant flavor group (tobacco vs. strawberry vanilla) by time (baseline to post-randomization) interaction effects on each odor image. For this analysis, only the 18 mg/ml nicotine content flavor groups will be included.

Exploratory Behavioral Aim: Determine if changes in flavor cue-reactivity are associated with changes in ECIG satisfaction, liking, craving, and dependence. One-sample t-tests will assess for anatomical regions where BOLD changes in odor cue-reactivity are correlated with changes in behavioral measures of e- cig satisfaction, craving, and dependence collected at the 2-week check-in and post-randomization visit, and changes in ECIG liking collected at the baseline and post-randomization visits.

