3.0 Inclusion and Exclusion Criteria

3.1 Inclusion Criteria

1. Aged 21-60
2. Smoke filtered cigarettes/machine-rolled cigarettes (≥ 5 cigarettes per day) or daily e-cigarette use for past year
3. No serious quit attempt in prior month. This includes use of any FDA approved smoking cessation medication (varenicline, bupropion [used specifically as a quitting aid], patch, gum, lozenge, inhaler, and nasal spray) in the past 1 month as an indication of treatment seeking.
4. Willing to supplement cigarette smoking with ECIG use for 4 weeks or replace e-cigarette with study product for 4 weeks
5. Willing to attend regular visits over a 4-week period (not planning to move, not planning extended vacation, no planned surgeries)

6. Willing to undergo two fMRI scans
7. Able to read and write in English
8. Able to understand and consent to study procedures
9. Access to computer with internet service that allows for use of Zoom

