7.4.6.3 Preparation and Dispensing

The unblinded study staff will be responsible for filling the cartomizers with the appropriate nicotine concentration (0mg/ml or 18 mg/ml) and flavor (tobacco or strawberry vanilla) in a biological safety cabinet. Filled cartomizers will be stored in bottles/bags with child-proof caps. Once filled, unblinded staff will then put cartomizer-containing bottle into ECIG kits

labelled with unique identifiers in order to track bottles and maintain blinding. Unblinded staff will appropriately package kits for the participants. At the randomization visit (Visit 2), participants will be randomly assigned a Randomization ID that matches a kit number. The blinded research assistants will not be involved in the packing and labelling of the kits. The blinded research assistant will be told what participant is assigned to which Randomization ID, which will maintain the blind.

7.4.6.4

Return or Destruction of the Test Article

Participants will be permitted to keep their ECIG device at the end of the study. Participants will be required to return all used and unused cartomizers to the research assistant at each clinic visit using provided containers/bags. Participants will not keep unused cartomizers at the end of the study. If a participant is withdrawn for medical reasons (CVD event), they will be asked to return their device/cartomizers via a pre-paid envelope to the study center.

7.4.6.5

Prior and Concomitant Therapy

Concomitant medications will be collected regularly throughout the trial to serve as covariates during analysis and to monitor participant health conditions. Medications related to certain medical conditions that are exclusions to the study, such as COPD and current heart conditions, will serve to alert the study staff of the presence of these conditions during screening.

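### The 18 vs 0 mg comparison ignores a baseline scan that could raise its power, and section 8.3 should say that contrast estimates, not z images, are differenced

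*Combined protocol and SAP*

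**What the plan says.** Section 8.3 defines the change measure in one sentence: "a difference z- statistic image will be calculated by subtracting the baseline image from the post-conditioning image". Three analyses use it.

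- **Aim 2, nicotine:** a two-sample t-test on "odor difference score z- statistic images comparing the 18 mg to 0mg nicotine content ECIG groups".
- **Aim 2, assigned vs unassigned flavor:** "A paired two-sample t-test will be conducted to compare the tobacco>rose and strawberry vanilla>rose odor difference score z-statistic image", run separately in each 18 mg/ml flavor group.
- **Aim 3:** a two-sample t-test, 18 mg/ml arms only, on "assigned flavor (strawberry vanilla or tobacco) > control rose difference score z- statistic images comparing the flavor groups".

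None of these models has a covariate. Section 7.4.3 stratifies randomization by gender, and 8.2 says this is to estimate gender effects for future research. Section 7.4.6.5 says: "Concomitant medications will be collected regularly throughout the trial to serve as covariates during analysis". Nothing in 8.3 takes that up.

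Aim 1 predicts that the odors differ before conditioning. For cigarette smokers and tobacco-flavor users, "We expect tobacco odor to elicit greater activation in the ventral striatum, amygdala, anterior insula, and OFC than the strawberry vanilla and rose". For fruit-flavor users, "We expect strawberry-vanilla odor to elicit greater activation in ventral striatum, amygdala, anterior insula, and OFC than tobacco and rose". Section 3.1 admits both kinds of user (cigarettes "or daily e-cigarette use for past year"), and user type is not a stratification factor.

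**The concern.** There are two separate issues.

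**Precision.** A t-test on change subtracts the baseline scan but does not use it as a predictor. In a randomized comparison this causes no bias. It can waste information, and section 8.2 claims only 60% power here.

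**Scale.** A z value is an estimate divided by its standard error (SE). If z images are subtracted, z moves when scan noise moves, even if activation does not. In 18 vs 0 mg both arms supply the same odor contrast, so a noise change common to everyone cancels. Aim 3 and the paired test set tobacco>rose against strawberry vanilla>rose. There a common noise change does not cancel if the mean baseline contrasts differ, and in Aim 3 randomization does not help because each arm contributes a different odor. Part of an apparent conditioning effect could then be scan noise.

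**Working it through.** **Inputs from the plan.** 56 randomized 1:1:1:1 (7.4.3), so 28 vs 28 for nicotine and 14 vs 14 for Aim 3; a medium effect size and 60% power (8.2).

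**Assumptions (the plan gives no figure).** d = 0.5; two-sided .10 applies to the 60% figure; scan-to-scan correlation r; ratio s of post to baseline SD; size of the noise change; baseline gap between odors; full retention.

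**Step 1. The plan's figure.** Noncentrality is 0.5 × √(28/2) = 1.871 on 54 df, giving 58.0% power at two-sided .10. This reproduces the stated 60% to within 2 points.

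**Step 2. Baseline adjustment.** With baseline SD 1 and post SD s:

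- Var(change) = 1 + s² − 2rs
- Var(adjusted) = s²(1 − r²)
- difference = (1 − rs)²

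So adjustment never increases the residual variance, and it gains nothing when rs = 1. With s = 1 the variance ratio is (1 + r)/2.

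| r | Variance ratio | Equivalent d = 0.5/√ratio | Noncentral t, 51 df | Full-model simulation (40,000 runs) |
|---|---|---|---|---|
| .3 | .65 | .620 | 74% | 73.5% |
| .5 | .75 | .577 | 69% | 68.2% |
| .7 | .85 | .542 | 64% | 63.5% |
| .9 | .95 | .513 | 60% | 59.4% |

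The simulation is slightly lower because it includes chance imbalance in the three covariates.

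Sensitivity to the SD ratio:

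- s = 1.25: 66/61/58/59% at the same r. At r = .8, rs = 1 and power is 57.5%, so nothing is gained.
- s = 0.8: 83/78/75/76%.

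Gender alone adds 0 to about 2 points (69.0% to 71.2% at r = .5 if it explains 10% of residual variance).

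**Step 3. Subtracting z images (only if that is what is done).** Let scan 2 have k times the SE of scan 1, with activation unchanged. Mean z then moves by (1/k − 1) times baseline z. Measurement error has SD 1 on the z scale at each scan, and between-subject SD is taken as 1. The SD of the z change is therefore √(2 + (1/k − 1)²). For Aim 3, noncentrality = gap × |1/k − 1| / (SD × √(2/14)) on 26 df. Rejection rates at nominal 5%, tobacco stronger at baseline:

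| Scan 2 noise | 1/k − 1 | SD | Gap 1 z | Gap 2 z | Pushed toward |
|---|---|---|---|---|---|
| 10% higher | −.091 | 1.417 | 5.3% | 6.2% | strawberry vanilla |
| 20% higher | −.167 | 1.424 | 6.0% | 9.2% | strawberry vanilla |
| 30% higher | −.231 | 1.433 | 7.0% | 13.0% | strawberry vanilla |
| 10% lower | +.111 | 1.419 | 5.5% | 6.9% | tobacco |
| 20% lower | +.250 | 1.436 | 7.3% | 14.4% | tobacco |
| 30% lower | +.429 | 1.478 | 11.5% | 31.5% | tobacco |

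Worked cell (30% higher, 2 z): 0.462 / (1.433 × 0.378) = 0.852, giving 13.0%. Simulation agrees (6.5/9.3/13.0% for the noisier scan at 2 z; 6.9/14.0/31.6% for the quieter). With no baseline gap the rate stays at 5%. Differencing contrast estimates also keeps it at 5%.

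**Step 4. What shrinks these rates.**

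- *Session-to-session variation* (SD 1 at each scan, assumed). For 30% higher noise and a 2 z gap, the variance becomes 2.053 + 1 + 1/1.3² = 3.645. Then SD = 1.909, noncentrality = 0.462 / (1.909 × 0.378) = 0.640, and the rate falls from 13% to about 9.5%. The 30% lower case falls from about 31% to 16%.
- *Fruit-flavor users who react oppositely.* With 2, 4 or 5 of 14 per arm, the 30% lower, 2 z rate falls from 32% to 18, 9 and 6%.

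**Step 5. Paired test (n = 14, odor and noise correlations .5).** At 10/20/30% lower noise, false positives are 6/9/17% at 1 z and 8.5/23/52% at 2 z. The direction depends on the arm: a quieter scan favors tobacco in both arms, so it resembles conditioning in the tobacco arm and its reverse in the strawberry vanilla arm. Both arms favored their assigned flavor in fewer than 0.1% of runs.

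**The case against.** **The wording may be loose rather than the method.** Section 8.3 could mean the z image of a within-subject post>baseline contrast. The noise problem then disappears. This stands, and it is why the second point is conditional.

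**A large noise change has no basis in the documents.** One scanner and sequence, the same tasks and the same 14-hour abstinence instruction apply at both scans. This stands: the 10 to 30% range is an assumption.

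**The unadjusted test is valid and the gain uncertain.** Also true. The case for adjustment is that the baseline scan is already acquired and little can be lost.

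**The baseline contrast is an image.** It has a different value at every voxel, so it is not one extra column. This stands and is reflected in the fix.

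Four stronger readings are tempting, but the documents do not support them.

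- *That the larger Aim 3 rates favor the hypothesis.* With tobacco stronger at baseline they arise from a quieter second scan and run against strawberry vanilla.
- *That a common noise change could reproduce the flavor-general claim of the paired test.* It cannot plausibly do so in both arms; one arm read alone can mislead.
- *That all between-subject results will be read at p<.10.* Section 8.2 says trends will be looked for, but attaches that threshold to the baseline flavor-group test. Using .10 in Step 1 is an assumption.
- *That Aim 1 guarantees a baseline gap.* It gives no size, its directions differ by user type and can offset each other, and the mix per arm is unknown.

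**Conclusion.** The point holds in a limited form and should be addressed.

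The firm part is that the 18 vs 0 mg test leaves out the baseline contrast and the gender stratum, and that 7.4.6.5 promises covariates that no model in 8.3 contains. On the assumptions above, adjustment moves power from 58% to between about 59 and 73% with equal scan variances. At worst it costs about 1 point.

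The conditional part is the z scale. If z images are subtracted, the error favoring the Aim 3 hypothesis is modest: about 5 to 7% at a 1 z gap and 6/9/13% at 2 z, against a nominal 5%. The quieter-scan rates reach 11% and 32%, in favor of tobacco. All are single-test figures, whereas the plan tests maps, and they do not estimate what this trial will show. The ambiguity itself is worth removing, because one reading is sound and the more natural one is not.

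**What to change.** In section 8.3:

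1. State that contrast estimates and their variances (FSL COPE and VARCOPE), not z images, are differenced and carried to the group level for Aims 2 and 3, including the paired test.
2. For 18 vs 0 mg, model the post-conditioning contrast on nicotine arm, with the baseline contrast (as a voxelwise or region-level regressor), assigned flavor and gender as covariates.
3. For Aim 3, keep the change in contrast estimates and add gender. Do not add the baseline contrast here, because the arms contribute different odors whose baseline means may differ by design.
4. Reconcile 7.4.6.5 with 8.3: name which pre-randomization medications enter which model, or remove the statement.

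**Cost.** Wording, 3 degrees of freedom in the nicotine model (54 to 51), somewhat more complex voxelwise modelling, and up to about 1 point of power where adjustment gains nothing (58.2% vs 57.5% in simulation at r = .8, s = 1.25). No new data or participants are needed. If contrast estimates are already differenced, item 1 is only a clarification.

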3.3 Early Withdrawal of Subjects

3.3.1 Criteria for removal from study

The Principal Investigator reserves the right to remove a participant from the study for any reason, based on their discretion.

Early Withdrawal Criteria Prior to Randomization: Participants who met any criteria below at Visit 2 will be considered for withdrawal prior to randomization:

1. Starting nicotine replacement therapy (e.g., patch, gum, lozenge, inhaler, nasal spray, Zyban, Chantix)
2. Use of other non-cigarette tobacco products in the past 7 days
3. Reporting a quit attempt in the past 7 days
4. Participant is not able to attend their Visit 2 Randomization visit within the study window.

General Withdrawal Criteria

1. Missing their study visit window: If a participant misses their study visit window, the participant will be considered for withdrawal from the study.
2. Not maintaining ECIG and cigarette use diary
3. New pregnancy: Participants who report a new pregnancy at any point during the study will be withdrawn.
4. Suicide attempt: If at any time during the study it is discovered that a participant has made a suicide attempt, they will be withdrawn from the study.
5. Cardiovascular disease (CVD) event requiring inpatient hospitalization: CVD typically includes MI (heart attack), PTCA (angioplasty/stenting), bypass surgery, stroke, peripheral vascular disease (arterial blockages in arms or legs leading to procedure or surgery). Less common CVD problems would be new cardiac arrhythmias (e.g., new atrial fibrillation) or new valvular disease (e.g., mitral or aortic regurgitation).
6. DVT/PE (deep vein thrombosis/pulmonary embolism, i.e., blood clots in the venous system) requiring inpatient hospitalization.
7. Psychiatric Inpatient Hospitalization: A participant will be withdrawn if he/she reports an inpatient hospitalization for psychiatric reasons at any time during participation in the study.
8. Participant choice: Participants may choose to remove themselves from the study by informing the research team in writing, by phone call or in person at any point during the study. If they choose to remove themselves from the study, they will not receive any further contact from the study center.
9. Adverse events related to ECIG use: Adverse events will be monitored at every study visit.
10. Worsening substance abuse in which the participant is behaving inappropriately at visits or demonstrates an inability to continue with the study.

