8.2 Sample size determination

For the proposed between-subject analyses, we will be looking for trends in the hypothesized direction, not statistical significance with traditional parametric statistics. With an estimated medium effect size, we will have approximately 50% power to find a liberal between-subject effect ($p<.10$) for the proposed t-test between the flavor groups on baseline cue-reactivity, 60% power to detect changes in cue-reactivity between the nicotine content and flavor groups, and 90% power to detect within-subject changes in cue-reactivity at $p<.05$. Groups will be stratified by gender to estimate gender effects for future research.

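### Aim 1 predicts opposite tobacco versus strawberry vanilla responses by user type, but its listed tests have no user-type term and omit the strawberry vanilla > tobacco contrast

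*Combined protocol and SAP*

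**What the plan says.** Section 3.1 admits cigarette smokers "or daily e-cigarette use for past year". It sets no quota by user type or usual flavor, and randomization (7.4.3) is balanced on gender and age only.

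Section 8.3, Aim 1, makes two predictions about the pre-conditioning scan:

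- Tobacco odor gives greater activation "than the strawberry vanilla and rose for combustible cigarette smokers and tobacco-flavored e-cigarette users".
- In the remaining user type the predicted order is the other way round: "We expect strawberry-vanilla odor to elicit greater activation in ventral striatum, amygdala, anterior insula, and OFC than tobacco and rose for fruit-flavored e-cigarette users".

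The analysis named is of the one-sample kind: "sample t-test will be conducted on the contrast of tobacco > strawberry vanilla, tobacco > rose, strawberry vanilla > rose". Its purpose is worded in one direction for each contrast; for tobacco the wording is: "identify anatomical brain regions where tobacco elicits greater neural activation over strawberry vanilla and rose odors". No user-type factor, subgroup or between-type comparison is given.

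Section 8.2 quotes about 50% power at p<.10, for a medium effect, for the "proposed t-test between the flavor groups on baseline cue-reactivity". Section 8.3 describes no such test. Where 8.3 uses the term flavor group, under Aims 2 and 3, it means the assigned product; for Aim 3, "only the 18 mg/ml nicotine content flavor groups will be included".

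**The concern.** The two predictions have opposite signs on tobacco versus strawberry vanilla, so a single mean over all participants cannot represent both. Two gaps follow.

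1. The strawberry vanilla > tobacco prediction in fruit-flavor users has no listed test, whether the tests are pooled or run within user type.
2. If the tests are pooled, the tobacco > strawberry vanilla map depends on a mix of user types that nobody has planned. A weak map could then mean no effect or cancellation. The fruit users' strawberry vanilla > rose prediction would also have no test of its own.

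Aim 1 analyzes the primary endpoint, odor cue-reactivity (1.2), and its wording names both smokers and e-cigarette users.

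**Working it through.** **Inputs.** From the documents: 56 randomized, 1:1:1:1, so 14 per arm (7.4.3); a medium effect and p<.10 for the baseline between-group test (8.2). Assumed, because the documents do not say: medium means 0.5 SD; within-type SD is 1; the test is in one region, not a map-wise search; all 56 have usable baseline scans; 0, 6, 11 or 17 of them are fruit-flavor users.

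**Step 1: the plan's own 50%.** Two-sample noncentral t, noncentrality = 0.5 × √(n₁n₂/(n₁+n₂)), alpha .10:

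| Groups | One-sided | Two-sided |
|---|---|---|
| 14 v 14 (the two 18 mg/ml arms) | 50.8% | 36.2% |
| 28 v 28 (flavor arms across nicotine levels) | 71.7% | 58.0% |
| 45 v 11 (a possible user-type split) | 57.7% | 43.1% |
| 39 v 17 (a possible user-type split) | 66.5% | 52.2% |

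The figure can be reproduced by the 18 mg/ml arms (one-sided) or by a user-type split (two-sided). It does not show which groups 8.2 means.

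**Step 2: pooled tobacco > strawberry vanilla.** Let f be the number of fruit users, with an effect of -0.5 SD in them and +0.5 SD in the rest.

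- Pooled mean = 0.5 × (56 - 2f)/56.
- Pooled SD ≈ √(1 + (56/55) × (f/56) × (1 - f/56)), because the spread between types inflates it.
- For f = 11: mean = 0.5 × 34/56 = 0.304; SD ≈ 1.077; standardized effect 0.282; noncentrality 0.282 × √56 = 2.11.

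Simulated power of the one-sample t-test at .05 (200,000 runs per case):

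| Fruit users of 56 | Pooled mean (SD units) | One-sided | Two-sided |
|---|---|---|---|
| 0 | 0.500 | 98% | 96% |
| 6 | 0.393 | 88% | 80% |
| 11 | 0.304 | 68% | 55% |
| 17 | 0.196 | 36% | 24% |

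Sensitivity to effect size, one-sided, same order: 72, 53, 37, 20% at ±0.3 SD; 100, 100, 95, 61% at ±0.8 SD.

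**Step 3: pooled rose contrasts.** These are diluted, not reversed. One-sided power at 6, 11 and 17 fruit users:

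- Tobacco > rose, 0.5 SD in smokers and tobacco-flavor users and none in fruit users: 95, 90, 81%.
- Strawberry vanilla > rose, 0.5 SD in fruit users: 10, 17, 28% if the others show no effect, but about 53, 60, 69% if they show 0.2 SD. The second set is not a test of the fruit-user prediction, because most of the signal then comes from the other users.

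**Step 4: tests within type.** In fruit users alone (own variance, one-sided .05), the listed tobacco > strawberry vanilla contrast rejects in at most 0.3% of samples. The unlisted reverse has 28, 46, 63% power at 6, 11, 17.

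**Step 5: a model with two user types.** Pooled variance, 54 df, two-sided .05, at 6, 11, 17 fruit users:

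- Fruit-user mean: 22.5, 37.0, 52.6%.
- 95% half-width, t(.975, 54)/√n: 0.82, 0.60, 0.49 SD.
- Smoker or tobacco-flavor mean: 93.5, 90.9, 86.6%.

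**The case against.** The strongest reply is that pooling is inferred. The predictions sit in the same paragraph as the tests and are stated by user type, so tests within type may have been meant. The power losses in Step 2 would then fall away. That stands as a limit on the size of the problem. It does not remove the gap: Aim 2 says explicitly when an analysis is run separately by group and Aim 1 does not, and strawberry vanilla > tobacco is missing either way.

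Next, that contrast is only the sign reversal of a listed one, and 8.3 says in general that the odors are compared with each other. True, so it is trivial to add, but the group-level list still omits it and no user-type term is supplied.

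Third, the baseline t-test in 8.2 may be the missing user-type comparison. Products are dispensed only at the end of the baseline visit (7.2.3), so randomized arms should differ then only by chance, and usual-flavor groups would be a more sensible target. This is fair. A reader might infer from the use of flavor group under Aims 2 and 3 that the 8.2 test certainly compares assigned arms; the documents do not establish that, and Step 1 does not settle it. What can be said is that its groups are undefined and 8.3 does not describe it.

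Last, this is a proof-of-concept study, and few fruit users may enrol: 15.6 bases feasibility on smokers, and 7.4.4 assumes continued cigarette use. That also stands. With 6 fruit users, pooled power is still 80% two-sided.

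**Conclusion.** The concern holds in a limited form. Aim 1 states predictions of opposite sign by user type, names no user-type term, and omits strawberry vanilla > tobacco on any reading. If the tests are pooled, two-sided power for tobacco > strawberry vanilla falls from 96% to 80, 55 and 24% with 6, 11 and 17 fruit users of 56. Those figures rest on an assumed user mix, equal and opposite 0.5 SD effects, and a single region.

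A reader might infer that Aim 1 as a whole will fail through cancellation. The documents do not support that: pooling is unstated, the fruit-user share is unknown and may be small, and the rose contrasts do not change sign. Aims 2 and 3 use post-minus-baseline images compared by nicotine level or by flavor, not by user type, and are unaffected. Severity is minor to moderate, rising with the fruit-user share.

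**What to change.** In 8.3, Aim 1:

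- Fit the group-level model with a user-type factor: smoker or tobacco-flavor e-cigarette user; fruit-flavor e-cigarette user.
- Fix in advance how dual users and other-flavor users are classified, and report them descriptively. Section 3.1 does not exclude people who do both. The pre-randomization withdrawal criterion in 3.3.1, "Use of other non-cigarette tobacco products in the past 7 days", does not say whether e-cigarettes count.
- Test only the predicted contrasts: tobacco > strawberry vanilla and tobacco > rose in the first type; strawberry vanilla > tobacco and strawberry vanilla > rose in the second. That is four tests. Crossing every contrast with every type would add tests that have no prediction behind them.
- State sidedness and report the number per type. Give the fruit-user result as an estimate with its 95% interval, because power there is low.
- Keep any pooled map or between-type comparison as secondary or exploratory. With 6 fruit users, the between-type test of a 1.0 SD difference has 62% two-sided power, against 80% for the pooled test.

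Confirm that the ECIG Use History form (Table 1) records usual flavor; the table gives form names only. In 8.2, name the groups that the baseline t-test compares and describe the test in 8.3, or delete it.

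The cost is plan wording, one sign-reversed contrast, a classification rule, 1 to 2 degrees of freedom, and possibly one questionnaire item. The fruit-user estimates will be imprecise, and dual or other-flavor users set aside will reduce the numbers in the tested types.
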